4.3 Sample Size and Power

Approximately 6,000 participants will be randomly assigned to vaccine in this study in a 1:1 ratio to receive either mRNA-1010 or an active comparator. With approximately 3,000 participants exposed to mRNA-1010, the study has approximately 95% probability to observe at least 1 participant with an AE at a true 0.1% AE rate.

Assuming approximately 15% of randomized participants will be excluded from the PP Immunogenicity Set, with approximately 5100 participants in the PP Immunogenicity Set (1:1 ratio; approximately 2550 in each vaccine group), this will provide at least 95% power to demonstrate non-inferiority of the immune response in all 4 strains, as measured by the GMT in participants receiving mRNA-1010 compared with that in the active comparator group, at a 2-sided alpha of 0.025 level, assuming an underlying GMR of 0.9 in all 4 strains and a non-inferiority margin of 1.5. The standard deviation of the natural log-transformed levels is assumed to be 1.5.

This sample size will also provide at least 95% power to demonstrate non-inferiority of the immune response in all 4 strains as measured by SCR in the mRNA-1010 group compared with that in the active comparator group, at a 2-sided alpha of 0.025 level, assuming a SCR of 70% in influenza A strains and 60% in influenza B strains, respectively, in the mRNA-1010 group (a

true rate difference is 0 compared to the active comparator group), and a non-inferiority margin of 10%.

4.4 Randomization

Randomization will be performed using a centralizing interactive response technology (IRT). and stratified by age categories (18 to < 50 years old, ≥ 50 to < 65 years old, or ≥ 65 years old) and influenza vaccine status in the prior 12 months (received or did not receive) at the time of screening. At least 50% of enrollees will be ≥ 50 years old, including approximately 20% who will be ≥ 65 years old. The Sponsor anticipates approximately 300 participants will be ≥ 75 years old.

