1. PROTOCOL SUMMARY

1.1 Protocol Synopsis

Name of Sponsor/Company: ModernaTX, Inc.	
Name of Investigational Product: mRNA-1010	
Protocol Title: A Phase 3, randomized, stratified, observer-blind, active-controlled study to evaluate the immunogenicity and safety of mRNA-1010 seasonal influenza vaccine in adults 18 years and older	
Protocol Number: mRNA-1010-P301 Amendment 2	
Study Period: Approximately 13 months per participant	
Phase of Development: Phase 3	
Estimated date first participant enrolled: June 2022	
Estimated date last participant completed: August 2023	
Total Number of Sites: Site Locations: approximately 50 sites across approximately 5 countries in Latin America and Asia-Pacific	
Objectives and Endpoints	
Objectives	Endpoints
Primary	

 To evaluate the humoral immunogenicity of mRNA-1010 relative to that of an active comparator against vaccine-matched influenza A and B strains at Day 29 	
 Geometric mean titer (GMT) at Day 29 as measured by hemagglutination inhibition (HAI) assay Proportion of participants reaching seroconversion at Day 29 as measured by HAI assay

 To evaluate the safety and reactogenicity of mRNA-1010 	
 Frequency and grade of each solicited local and systemic reactogenicity adverse reaction (AR) during a 7-day follow-up period post vaccination

	
 • Frequency and severity of any unsolicited adverse events (AEs) during the 28-day follow-up period post vaccination • Frequency of any serious AEs (SAEs), AEs of special interest (AESIs), medically attended AEs (MAAEs), and AEs leading to discontinuation from Day 1 through Day 361 (Month 12)/end of study (EoS)
Secondary	

 • To further evaluate the immunological response of mRNA-1010 (for superiority) relative to an active comparator against vaccine-matched influenza A virus strains at Day 29 	
 • GMT at Day 29 as measured by HAI assay • Proportion of participants reaching seroconversion at Day 29 as measured by HAI assay

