6. STUDY TREATMENT

6.1 Investigational Product and Active Comparator Administered

The term “IP” refers to the mRNA-1010 vaccine and to the licensed seasonal influenza vaccine (the “active comparator”) administered in this study. The vaccines to be administered in this study are described in [Table 4](#).

The mRNA-1010 vaccine to be tested includes mRNAs encoding for the surface Has of the influenza strains recommended by the WHO for 2022 SH cell- or recombinant-based vaccines:

- A/Wisconsin/588/2019 (A/H1N1)-like virus;
- A/Darwin/6/2021 (A/H3N2)-like virus;
- B/Michigan/01/2021 (B/Victoria lineage)-like virus; and
- B/Phuket/3073/2013 (B/Yamagata lineage)-like virus.

mRNA-1010 is formulated in LNPs composed of 4 lipids (1 proprietary and 3 commercially available): the proprietary ionizable lipid SM-102; cholesterol; 1,2-distearoyl-sn-glycero-3-phosphocholine (DSPC); and 1-monomethoxypolyethyleneglycol-2,3-dimyristylglycerol with polyethylene glycol of average molecular weight 2000 (PEG2000-DMG). The mRNA-1010 injection is provided as sterile liquid for injection and is a white-to-off-white dispersion at a concentration of 0.1mg/mL in CCI Tris buffer containing CCI sucrose and CCI sodium acetate at pH 7.0 – 8.0.

The mRNA-1010 vaccine will be administered as a single 0.5 mL IM injection at an mRNA total dose level of 50 µg to participants according to the vaccination group assignment ([Table 4](#)).

The active comparator administered in this study is a licensed quadrivalent inactivated seasonal influenza vaccine (Fluarix Tetra) administered as a single 0.5 mL IM injection ([Table 4](#)).

Table 4: Investigational Product and Active Comparator Administered

Vaccination Group:	Investigational Product	Active Comparator
Intervention Name:	mRNA-1010	Fluarix Tetra (S-Hemisphere)
Type	Vaccine	Vaccine
Dosage Level(s):	50 µg (mRNA)	60 µg (protein)
Route of Administration:	IM injection	IM injection
Physical Description:	Sterile liquid for injection, white-to-off-white dispersion	Sterile, colorless, and slightly opalescent suspension
Source:	Provided centrally by the Sponsor	Hybrid – Potentially Centrally and Locally

Packaging and Labeling:	mRNA-1010 will be provided in 2R glass vials. Each vial will be labeled as required per country requirement.	Active comparator will be provided in a prefilled syringe in a carton. Each carton will be labeled as required per country requirement.
--------------------------------	--	---

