6.3.1.1 Primary Analysis

- Analysis of GMTs of anti-HA antibodies as measured by HAI against vaccine-matched influenza A and B strains at Day 29

An analysis of covariance model (ANCOVA) will be performed using the log-transformed HAI titers against a specific vaccine-matched strain at Day 29 as the dependent variable, vaccination group as the fixed variable, log-transformed baseline HAI titers as a fixed covariate, adjusting for the stratification factors. The geometric least square mean (GLSM), and its corresponding 95% CI results in log-transformed scale estimated from the model will be back-transformed to obtain these estimates in the original scale, as an estimate of the GMT for each vaccination group.

The GMR for mRNA-1010 vs. active comparator, estimated by the ratio of GLSM and the corresponding 2-sided 97.5% CI will be provided to assess the vaccine difference and calculated by back-transforming of the difference estimated from the ANCOVA model. The corresponding 2-sided 97.5% CI of GMR will be provided to assess the difference in immune response between the mRNA-1010 compared to the active comparator group at Day 29. For each strain, the non-inferiority of GMT will be considered demonstrated if the lower bound of the 97.5% CI of the GMR is > 0.667 based on a non-inferiority margin of 1.5. Refer to Immune Estimand 1a in [Table 12](#).

Descriptive statistics (n, median, min, max) will also be provided for the GMT of HAI titers with corresponding 95% CI at each timepoint. The 95% CIs will be calculated based on the t-distribution of the log-transformed values then back transformed to the original scale for presentation. In addition, the GMT with corresponding 95% CI will be plotted at each time point respectively.

- Analysis of SCR against vaccine-matched influenza A and B strains as measured by HAI at Day 29

The number and percentage of participants with seroconversion due to vaccination will be provided with 2-sided 95% CI using the Clopper-Pearson method at Day 29. To compare the

seroconversion rates between the vaccination groups, the Miettinen-Nurminen's method will be used to calculate the 97.5% CI for the difference in SCR. Refer to Immune Estimand 2a in [Table 12](#). For each strain, the non-inferiority of SCR will be considered demonstrated if the lower bound of the 97.5% CI of the SCR difference is $> -10\%$ based on a non-inferiority margin of 10%.

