6.3.1.3 Subgroup Analysis

To assess the consistency of immunogenicity response of mRNA-1010 across subgroups, subgroup analysis of the co-primary endpoints will be conducted by subgroups defined by age group 1, age group 2, prior influenza vaccine status, race, sex, and BMI category (see [Table 5](#)), based on PP Immunogenicity Set. For each subgroup category, the co-primary immunogenicity endpoints will be analyzed using the same statistical methods as for primary analysis. Additional details are documented in [Section 4.2](#).

If the number of participants in a subgroup is less than 10% of sample size in the analysis set, it may be combined with other subgroups for the subgroup analyses.

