Target Population	Adults aged 18 years or older who receive the assigned IP administration, complied with immunogenicity blood sampling to have a baseline and at least 1 post-injection serum antibody assessment as measured by HAI assay after the IP administration, and have no significant protocol deviations impacting the immune response and RT-PCR-confirmed influenza between Days 1 to 29.	Adults aged 18 years or older who receive any IP administration and complied with immunogenicity blood sampling to have a baseline and at least 1 post-injection antibody assessment as measured by HAI assay.
Endpoint	GMT ratio of anti-HA levels on Day 29	As per Estimand 1a.
Treatment Conditions	mRNA-1010 vs. active comparator (Fluarix Tetra)	As per Estimand 1a.

Population-Level Summary	Immune response to seasonal influenza defined as GMT ratio of anti-HA level as measured by HAI assay using an ANCOVA model on the log-transformed tiers on Day 29, with the vaccination group as the fixed variable, adjusted for stratified age group used for randomization and log-transformed baseline tiers.	As per Estimand 1a.
Intercurrent Event Strategy		
IcEv1 (early discontinuation or unrelated death)	Principal stratum	Principal stratum
IcEv2 (alternative influenza vaccine)	Principal stratum	Treatment policy
IcEv3 (COVID-19 vaccine)	Principal stratum	Treatment policy
IcEv4 (prohibited medications)	Principal stratum	Treatment policy
IcEv5 (early infection)	Principal stratum	Treatment policy
IcEv6 (wrong vaccination)	Principal stratum	Treatment policy

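### Country is recorded for everyone but is in neither the Day 29 GMT model nor the consistency subgroups, so no planned output would show a country-specific difference; the effect on precision is small and the primary noninferiority tests are unaffected.

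*SAP*

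**What the plan says.** - **Setting.** Protocol 1.1 plans "approximately 50 sites across approximately 5 countries in Latin America and Asia-Pacific".
- **Randomization.** SAP 4.4 stratifies by age category (three levels) and by "influenza vaccine status in the prior 12 months (received or did not receive) at the time of screening". Country is not a factor.
- **GMT model.** The ANCOVA in SAP 6.3.1.1 has vaccination group, "log-transformed baseline HAI titers as a fixed covariate, adjusting for the stratification factors". Protocol 9.5.1 gives the same model. Table 12 in SAP 9.8 is narrower: "adjusted for stratified age group used for randomization and log-transformed baseline" titers, with no mention of prior vaccination.
- **Seroconversion.** The rate difference uses the Miettinen-Nurminen interval, with no covariates (SAP 6.3.1.1).
- **Consistency.** SAP 6.3.1.3 sets out to check that the immune response is consistent, using "subgroups defined by age group 1, age group 2, prior influenza vaccine status, race, sex, and BMI category". It allows a subgroup with less than 10% of the analysis set to be combined with others. Table 5 has no country or region row.
- **Country.** SAP 6.2.2 lists it among the baseline characteristics to be tabulated. No other planned analysis in the text names it.
- **Supply.** In Protocol 6.1, Table 4, mRNA-1010 is supplied centrally by the sponsor. The comparator's source is given as "Hybrid – Potentially Centrally and Locally".

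**The concern.** The protocol calls the trial pivotal and in support of licensure, and it uses the Day 29 response to infer efficacy. A reader will ask whether the result holds in each country. Countries may differ in influenza exposure and vaccination history, and the route of comparator supply may differ too. The SAP states a consistency aim but leaves out the one recorded variable that would address this question directly.

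Two things are at stake. First, a pooled GMR or seroconversion difference could average over a country where the comparison looks quite different, and no planned output would reveal it. A country table made after unblinding would be open to the charge of being post hoc. Second, any variation in titer between countries that baseline titer, age and prior vaccination do not explain stays in the residual error. That could matter for the A-strain superiority test (H3, GMR above 1) and super-superiority test (H4, GMR above 1.5). Each must succeed on both A strains before the sequence continues.

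**Working it through.** **Inputs from SAP 4.3:** 2550 per arm, SD 1.5 on the natural log scale, true GMR 0.9, GMT bound 0.667, seroconversion 70% (A) and 60% (B) with true difference 0 and margin 10 points, and testing "at a 2-sided alpha of 0.025 level" (z = 2.241).

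**Assumed, because the documents give no figure:** the share R² of residual variance explained by country (1%, 5%, 10%), the true GMR for H4, and country sizes.

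**1. The plan's own power figure**

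SE of ln GMR = 1.5 × √(2/2550) = 0.0420.

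- GMT, per strain: Φ(ln(0.9/0.667)/0.0420 − 2.241) = Φ(0.2996/0.0420 − 2.241), above 99.999%. For all four strains, treated as independent, it is still above 99.999%.
- Seroconversion: Φ(0.10/√(2p(1−p)/2550) − 2.241), above 99.999% at both p = 0.70 and p = 0.60.

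The stated figure of at least 95% is met with a wide margin, so adjusting for country cannot visibly change noninferiority power.

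**2. Precision for H4**

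Adding country multiplies the SE by √(1−R²). Take a true GMR of 1.65 and a two-sided 5% level, which applies if noninferiority holds for both A and B strains. Power per strain = Φ(ln(1.65/1.5)/SE − 1.96).

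| R² | SE multiplier | Equivalent total n, 5100/(1−R²) | H4 power per strain | Gain (points) |
|---|---|---|---|---|
| 0 | 1 | 5100 | 62.13% | – |
| 1% | 0.995 | 5152 | 62.56% | 0.4 |
| 5% | 0.975 | 5368 | 64.35% | 2.2 |
| 10% | 0.949 | 5667 | 66.70% | 4.6 |

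At a true GMR of 1.70, power goes from 84.6% to 85.0%, 86.4% and 88.1%. Since 1.65/1.5 = 1.10, the table also applies to H3 at a true GMR of 1.10.

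**3. What could go unseen**

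Suppose one country holds 20% of participants with a true GMR of 0.60, and the rest have 0.90.

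- Pooled GMR = exp(0.2 × ln 0.60 + 0.8 × ln 0.90) = 0.830.
- Probability of passing the GMT test, per strain = Φ(ln(0.830/0.667)/0.0420 − 2.241) = 99.8%.

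**4. Would a country display be informative?**

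- Five equal countries, 510 per arm each: the 95% interval multiplies and divides the GMR by exp(1.96 × 1.5 × √(2/510)) = 1.20. At 70% seroconversion the half-width is 1.96 × √(2 × 0.21/510) = 5.6 points.
- A country at the 10% pooling limit, 255 per arm: factor 1.30 and half-width 8.0 points.
- One country with 20% of participants against the rest: a GMR ratio of exp(2.80 × 1.5 × √(2/510 + 2/2040)) = 1.34 is detectable with 80% power.

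**5. Chance imbalance**

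For a country with 20% of participants, the 95% range for the difference in its share between arms is 1.96 × √(0.2 × 0.8 × 2/2550) = ±2.2 points.

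**The case against.** The strongest case is that nothing here is an error. Allocation is 1:1 through a central system, so leaving country out biases neither the estimate nor the test, and the model in SAP 6.3.1.1 matches the stratification. No rule in either document asks for a country analysis. All of this stands.

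The precision argument also rests on chosen inputs. The R² values come from nowhere in the documents, and they must be variance explained beyond baseline titer, which may already absorb part of any country effect. The SD of 1.5 is given for log-transformed levels, not for the ANCOVA residual. The trial is not sized for H4, and a GMR of 1.65 was picked where power is sensitive. This stands too, and it makes the power table an illustration only.

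A reader might infer from Table 4 that the control vaccine differs between countries. The documents do not support that. The row describes sourcing of one named licensed product; it says neither that source varies by country nor that locally sourced product behaves differently. A country subgroup would not isolate source in any case.

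Race is already a planned subgroup, and Protocol 9.5.1 leaves room for other subgroup analyses. But race is only a partial proxy for country, and the SAP list that puts the protocol's allowance into effect omits country.

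Finally, changing the primary model is more than a wording edit. Protocol 9.5.1 carries the same model, and SAP 1 describes its own modifications as not principal in nature, even though it also says the SAP prevails where methods differ. This stands, and it is a reason to allow a sensitivity model instead.

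**Conclusion.** The point holds as a minor improvement, mainly for the consistency check. No planned analysis would show a country-specific difference in the co-primary endpoints. Under the assumed 20% country at GMR 0.60 with 0.90 elsewhere, the pooled GMT test would pass about 99.8% of the time per strain without any sign of it. With roughly equal countries the display would be precise enough to be worth reading.

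The precision loss is real in direction but of unknown size. The range of about 0.4 to 4.6 points of per-strain H4 power assumes SD 1.5, a true GMR of 1.65, a two-sided 5% level and R² of 1% to 10%.

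Two stronger readings fail. The primary result is not biased or underpowered: randomization balances country apart from chance, and noninferiority power is about 100% on the plan's inputs. Nor is a country analysis something the documents oblige the sponsor to do; it follows from the SAP's own consistency aim as a matter of judgement. The difference in covariates between SAP 6.3.1.1 and Table 12 is a separate inconsistency in the text and needs no assumption.

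**What to change.** Before the database lock for the Day 29 analysis:

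1. Add country, or region where countries are small, to Table 5 and SAP 6.3.1.3 for the co-primary endpoints, using the existing 10% pooling rule. State that it is descriptive.
2. Add country as a fixed factor in the SAP 6.3.1.1 ANCOVA, carried through to H3 and H4. If the sponsor prefers to keep the Protocol 9.5.1 model, prespecify the country-adjusted ANCOVA as a sensitivity analysis.
3. In the same edit, make the covariates in SAP 6.3.1.1 and Table 12 agree, including whether prior vaccination status is in the model.

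Randomization and data collection do not change. The cost is about 4 degrees of freedom in about 5100 participants and one more subgroup row, with wider intervals by country (a factor of about 1.20 to 1.30 on the GMR in the cases above). If the primary ANCOVA is changed, the departure from the protocol model should be recorded in SAP 7, which now lists no changes.

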4.5 Blinding and Unblinding

This study is an observer-blind study. The investigator, clinic staff, study participants, site monitors, and Sponsor personnel (or its designees) will be blinded to the IP administered until the study database is locked and unblinded for the final analysis with certain exceptions, please refer to Section 6.2 of the protocol for details. More details of blinding and unblinding processes are specified in the study data blinding plan.

Planned analyses are described in [Section 6.8](#) of this SAP and Section 9.6 in the Protocol Amendment 2. At the primary analysis and other pre-planned analyses, pre-identified Sponsor team members and selected contract research organization (CRO) team members as specified in the study data blinding plan will be unblinded to conduct the analyses. After unblinding, this team will not participate in the conduct or execution of the subsequent course of the study. Meanwhile, a separate blinded biostatistics and programming team will be in place until the database lock for the Final Analysis. Participants and investigators will remain blinded until the end of this study.

An external Data Safety Monitoring Board (DSMB) will conduct safety review of study data to safeguard the interests of clinical study participants and to enhance the integrity of the study. The DSMB will review safety data up to 7 days post-vaccination from the first 500 enrolled participants and safety data up to 28 days post-vaccination from all participants, provided by the

independent unblinded statistician who has no other responsibilities associated with study design or study conduct.

5 Analysis Sets

Analysis sets for statistical analyses are Randomization Set, Full Analysis Set (FAS), Modified Intent-to-Treat (mITT) Set, PP Set for Efficacy, Immunogenicity Set, PP Immunogenicity Set, Solicited Safety Set, and Safety Set.

Randomization Set

The Randomization Set consists of all participants who are randomly assigned to treatment, regardless of the participants' vaccination status in the study. Participants will be analyzed according to the group to which they are randomized to.

Full Analysis Set

The FAS consists of all participants who are randomized and receive any study vaccination. Participants will be analyzed according to the group to which they are randomized to.

Modified Intent-to-Treat Set

The mITT Set consists of all participants in the FAS who provide any follow-up for ILI beginning at least 14 days following administration of study intervention. Participants will be analyzed according to the group to which they are randomized to.

The mITT Set is the primary population for the analysis of efficacy data.

PP Set for Efficacy

The PP Set for Efficacy consists of all participants in the mITT Set who have no significant protocol deviations that impact key or critical efficacy data. Participants will be analyzed according to the group they are randomized to.

Immunogenicity Set

The Immunogenicity Set consists of all participants in the FAS who have baseline and Day 29 antibody assessment via HAI assay. Participants will be analyzed according to the group to which they were randomized.

PP Immunogenicity Set

The PP Immunogenicity Set includes all participants in the Immunogenicity Set who received planned dose of IP, complied with the immunogenicity testing schedule, and had no significant protocol deviations that impact key or critical data. Participants with RT-PCR-confirmed influenza between Days 1 to 29 will be removed from the PP Immunogenicity Set.

The PP Immunogenicity Set is the primary population for the analysis of immunogenicity data in the study unless specified otherwise. Participants will be analyzed according to the group to which they are randomized to.

For PP Set for Efficacy and PP Immunogenicity Set, the following major dosing error ranges for planned mRNA-1010 and active comparator will be used to determine participant exclusion from the analysis populations:

Table 3 Exclusion Criteria for Dosing Errors

Actual Vaccine Received	Planned (mRNA-1010 50 µg)
mRNA-1010 ≤ 37.5 µg	Yes ¹
mRNA-1010 >37.5 µg – 62.5 µg	No
mRNA-1010 > 62.5 µg	Yes
Active Comparator ²	Yes

1. Yes means major dosing error
2. Active comparator is Fluarix Tetra (pre-filled syringe)

Table 4 Major Dosing Errors for Active Comparator

Actual Vaccine Received	Planned (Active Comparator²)
Fluarix Tetra ≤ 45 µg	Yes ¹
Fluarix Tetra > 45 µg – 60 µg	No
Any mRNA-1010	Yes

1. Yes means major dosing error
2. Active comparator is Fluarix Tetra (pre-filled syringe)

Solicited Safety Set

The Solicited Safety Set consists of all randomized participants who received any study vaccination and contributed any solicited AR data, i.e., had at least one post-baseline solicited safety assessment.

The Solicited Safety Set will be used for the analyses of solicited ARs, and participants will be included in the vaccination group corresponding to the actual vaccine that they received.

Safety Set

The Safety Set includes all participants who were randomized and received any study vaccination.

The Safety Set will be used for all analyses of safety except for the solicited ARs. Participants will be included in the vaccination group corresponding to the actual vaccine that they received.

For Solicited Safety Set and Safety Set, the following dosing ranges will be used to determine participant's actual vaccination group:

- mRNA-1010 50 µg group: If the received dose of mRNA-1010 is > 0 µg
- Fluarix Quadrivalent 60 µg group: If the received dose of active comparator (Fluarix Tetra) is > 0 µg and mRNA-1010 is 0 µg

6 Statistical Analysis

